8.9 Proof-of-Concept Composite Endpoint Analysis

Finkelstein-Schoenfeld Analysis

The proof-of-concept efficacy analysis uses a hierarchical combination applying the method of Finkelstein-Schoenfeld (Finkelstein 1999) to the following:

- 1. All-cause mortality at Day 30 Visit, and
- 2. Severe respiratory failure through the Day 30 Visit, and
- 3. Pancreatic necrosis ≥30% through the Day 30 Visit, and
- 4. Rehospitalization for AP or pancreatic necrosis/necrotizing pancreatitis through the Day 30 Visit, and
- 5. Time to solid food tolerance within 30 Days of the SFISD

The test score will be computed using a pairwise ranking procedure. The test statistic will be based on the sum of these scores and was stratified by the eCRF recorded sex (male or female) and then the stratification factor of the risk for organ failure (higher or lower) based on eCRF data.

Within each stratum, each subject will be compared to every other subject in a pair-wise manner. The pair-wise comparison assigned a +1 to the "better" subject and a -1 to the "worse" subject. All-cause mortality will be given higher priority in the calculation and only when two given subjects are alive at Day 30 when evaluating on all-cause mortality, then persistent severe respiratory failure, pancreatic necrosis >30%, rehospitalization for AP, and time to solid food tolerance would be used in the comparison in sequence.

- If one subject is alive and the other is not, the live subject receives a +1 and the deceased one a -1.
- If both subjects died, then the comparison is a tie.
- If both subjects are alive, then the comparison evaluates persistent severe respiratory failure to assign scores. The subject with persistent severe respiratory failure receives a -1 while the other without persistent severe respiratory failure receives +1.
- If both patients have, or do not have, persistent severe respiratory failure, then the comparison evaluates pancreatic necrosis ≥30%. The subject with pancreatic necrosis \geq 30% receives a -1 while the other without pancreatic necrosis 30% receives +1.

Protocol CM4620-203 CONFIDENTIAL Page 24 of 31

- If both subjects have, or do not have, pancreatic necrosis ≥30%, then the comparison evaluates rehospitalization for acute pancreatitis. The subject with rehospitalization for acute pancreatitis receives a -1 while the other without rehospitalization for acute pancreatitis receives +1.
- If both subjects have, or do not have, rehospitalization for acute pancreatitis, the comparison uses time to solid food tolerance to assign scores. The subject with the longer time to solid food tolerance receives a -1 while the other with shorter time to solid food tolerance receives +1.

No imputation will be done for missing cases for the proof-of-concept composite efficacy analysis based on the Finkelstein-Schoenfeld method. In case when one subject is censored and all-cause mortality, persistent severe respiratory failure, pancreatic necrosis ≥30%, rehospitalization for AP, or time to solid food tolerance are unknown, the unknown status will be used in calculating the score and the score will be considered 0.

The proposed test is a score test based on the sum of the scores for the treated group. The test statistic can be written as

$$T = \sum_{k} \sum_{i \in A_k} D_i U_i$$

 A_k is the set of the subjects in the kth strata and U_i is the score calculated within each stratum. D_i =1 for subjects in Auxora group and D_i =0 for subjects in placebo group. K=1,2,3,4 for four strata. The variance is written as

$$V = \sum_{k} \frac{m_{k}(n_{k} - m_{k})}{n_{k}(n_{k} - 1)} (\sum_{i \in A_{k}} U_{i}^{2})$$

 M_k is the total number of Auxora subjects in the kth stratum. N_k is the total number of subjects in the kth stratum.

The hypothesis will be tested by comparing T/\sqrt{V} .

Win Ratio and Confidence Interval

The win ratio method involves a comparison of each patient in an active treatment group with each patient in the placebo group to determine whether the active treatment patient had a better outcome (a "win"), a worse outcome (a "loss"), or an identical outcome (a "tie"). Each comparison begins with the death outcome and proceeds through the hierarchically ordered set of outcomes described below until the first outcome is identified for which the outcomes differ between the patients; this outcome is used to determine the "win" or "loss." The win ratio is the total number of wins divided by the total number of losses, and a win ratio >1 indicates better outcomes with active treatment.

Categories (a), (c), (e), (g), and (i) represent Auxora wins based on all-cause mortality, persistent severe respiratory failure, pancreatic necrosis >30%, rehospitalization for AP, and time to solid

Protocol CM4620-203 CONFIDENTIAL Page 25 of 31

food tolerance sequentially. Similarly, categories (b), (d), (f), (h), and (j) represent placebo wins. Category (k) represents ties, pairs where subjects were not able to be differentiated.

- (a) Death on placebo, but alive on Auxora at Day 30
- (b) Death on Auxora, but alive on placebo at Day 30
- (k) Death on placebo, death on Auxora at Day 30. No further comparisons will be performed.

If alive on placebo and alive on Auxora at Day 30:

- (c) Severe respiratory failure on placebo but not on Auxora
- (d) Persistent severe respiratory failure on Auxora but not on placebo

If a tie for severe respiratory failure:

- (e) Pancreatic necrosis ≥30% on placebo but not on Auxora
- (f) Pancreatic necrosis ≥30% on Auxora but not on placebo

If a tie for pancreatic necrosis $\geq 30\%$:

- (g) Rehospitalization for AP on placebo but not on Auxora
- (h) Rehospitalization for AP on Auxora but not on placebo

If a tie for rehospitalization for AP:

- (i) Earlier time to solid food tolerance on Auxora
- (j) Earlier time to solid food tolerance on placebo

If a tie for rehospitalization for AP

(k) Tie for all outcomes

The overall win ratio will be calculated by adding (a) + (c) + (e) + (g) + (i) for all 4 strata and dividing it by the sum of (b) + (d) + (f) + (h) + (j) across all 4 strata.

The standard error of log (Win Ratio) can be calculated as: SE (Log Win Ratio) = log (Win Ratio) / Z score from FS method The confidence interval can be computed as follows: 95% CI for Win Ratio = exp (log (Win Ratio) +/- 1.96 * SE (Log Win Ratio))

The Win Ratio with 95% CI and p-value based on Finkelstein-Schoenfeld method will be used to compare each Auxora group versus placebo group.

The proof-of-concept analysis will perform a sensitivity analysis that will combine the subjects from the 1.25 mL/kg and 0.625 mL/kg groups into one combined group and combine the subjects from the 0.3125 mL/kg and placebo groups into a second combined group. The two combined groups will be compared using the Finkelstein-Schoenfeld method and Win Ratio method (Finkelstein 1999). This grouping method assumes that the 1.25 mL/kg and 0.625 mL/kg groups have the similar treatment effect on persistent severe respiratory failure. If this assumption is not valid after the primary analysis of the time to solid food tolerance after the database lock, the grouping method may be adjusted.

Protocol CM4620-203 CONFIDENTIAL Page 26 of 31

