8.11 Discharge Date

The time and date of discharge will be recorded as well as if the patient meets criteria for medically indicated discharge. All patients will be trained to complete the mGCSI-DD and will complete the mGCSI-DD before leaving the hospital. If patients are discharged on Days 25-29, they may complete the Day 30 assessments on the day of discharge. Following discharge, the Investigator or designee should contact patient by telephone once per week to confirm diary completion and patient agrees to return for Day 30 visit.

If a patient is admitted to a hospital following discharge but prior to Day 30 visit, Investigator will report the reason for the hospitalization as per serious adverse event reporting guidelines (See Section 9.2 and Section 9.7). As the patient is still within the study period, investigators or designee should resume collection of study procedures as per Schedule of Events (See Appendix 8). If patient is not admitted to the hospital where the study is being conducted, investigators are asked to record any procedures (i.e., invasive mechanical ventilation) received while patient was admitted during the study period within an unscheduled procedures form in the eCRF.

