8.7.3 Length of Stay in the Hospital

The number of days patients are in the hospital from the SFISD, including ICU stay and readmissions for any etiology, during the 30 Days of the study will be summarized by treatment groups and compared between each Auxora treatment group and placebo group using an analysis of variance model, which includes treatment group, the stratification factor of the eCRF recorded sex (male or female), and then the stratification factor of the risk for organ failure (higher or lower) based on eCRF data as the fixed effects in the model. The proportion of patients in each quartile of hospital stay (1-7 days, 8-14 days, 15-21 days, and 22-30 days) and the patients who remain hospitalized at Day 30 will also be summarized by treatment groups.

Two sets of analyses will be conducted. The first analysis is to assess patient benefit; the number of days in the hospital will be defined as 30 if the patient dies due to acute pancreatitis (composite strategy). The second analysis is to assess healthcare systems benefit; the number of days in the hospital before the patient's death will be used in the analysis (while alive strategy).

8.7.4 Re-hospitalization for acute pancreatitis (AP) Through Day 30

The date of each re-hospitalization and the reasons for re-hospitalizations will be collected for each patient. The proportion and 95% CI of patients who are re-hospitalized for either acute pancreatitis or the development of pancreatic necrosis/necrotizing pancreatitis through the Day 30 visit will be displayed using a Clopper-Pearson interval and will be compared between each Auxora treatment group and placebo group using a Cochran-Mantel-Haenszel test stratified by the sex (male or female) and the risk for organ failure (higher or lower) based on eCRF data. Prohibited immunosuppressive medications or immunotherapies and treatment discontinuation will be ignored (treatment policy strategy). If the re-hospitalization for acute pancreatitis status is unknown, the re-hospitalization for acute pancreatitis will be imputed as No.

The proportion and 95% CI of patients who are re-hospitalized for other causes through Day 30 will also be analyzed in a similar manner.

Protocol CM4620-203 CONFIDENTIAL Page 20 of 31

8.7.5 Change in Severity of AP by CTSI Score from Screening to Day 30

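### Tier 4 of the SAP 8.9 composite ranks a patient still in the index hospital stay at Day 30 above one who went home and was readmitted for AP; the net effect is small and conditional, and one sentence removes it

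*SAP*

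**What the plan says.** SAP 8.9 compares patients pairwise on five components in order: death, severe respiratory failure, pancreatic necrosis of at least 30%, rehospitalization, and time to solid food tolerance. A pair is decided at the first component on which the two differ. Tier 4 is listed as "Rehospitalization for AP or pancreatic necrosis/necrotizing pancreatitis through the Day 30 Visit" and scored thus: "The subject with rehospitalization for acute pancreatitis receives a -1 while the other without rehospitalization for acute pancreatitis receives +1". The win ratio repeats the rule. Category (g), an Auxora win, is "Rehospitalization for AP on placebo but not on Auxora", and category (h), a placebo win, is "Rehospitalization for AP on Auxora but not on placebo".

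Protocol 8.11 describes a readmission as something that comes after discharge: "If a patient is admitted to a hospital following discharge but prior to Day 30 visit". The only exception within the composite is for a censored patient with unknown status, where "the unknown status will be used in calculating the score and the score will be considered 0".

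The plan does foresee patients who are never discharged. SAP 8.7.3 counts all hospital days, readmissions included, "and the patients who remain hospitalized at Day 30 will also be summarized by treatment groups". SAP 8.7.1 counts such a patient as not tolerating solid food at the end of study. SAP 8.7.4 reports the proportion of "patients who are re-hospitalized for either acute pancreatitis or the development of pancreatic necrosis/necrotizing pancreatitis through the Day 30 visit". It names no special denominator, so the default in SAP 8.1.3 applies: everyone in the treatment group.

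**The concern.** A patient in hospital for the whole 30 days has not been at risk of readmission, yet tier 4 puts that patient in the better class. Someone who ate early, went home and came back briefly for AP loses to someone who never left. Because tier 4 settles the pair, a much later first solid meal in the second patient has no influence.

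That ordering runs against what the composite is meant to express. If an effective dose empties beds sooner, it has fewer never-discharged patients, so more of the reversed pairs go against it than for it. Each dose receives a Finkelstein-Schoenfeld p-value and a win ratio with confidence interval from this scoring, so the rule feeds directly into reported results.

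**Working it through.** **The pair, scored as written.** Take two living patients without severe respiratory failure or necrosis of at least 30%.

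- Patient 1: first tolerated solid meal at 60 h, discharged, readmitted for AP.
- Patient 2: first tolerated solid meal at 600 h, still in the index stay at Day 30.

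Tier 4 gives patient 1 a score of -1 and patient 2 a score of +1, and tier 5 is not reached. Had patient 1 not been readmitted, tier 4 would tie and patient 1 would win on tier 5. The score-0 rule does not help: patient 2 was under observation throughout, so the readmission status is known to be no.

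**Inputs.** There are 54 patients per arm (SAP 4), so 54 x 54 = 2,916 Auxora-placebo pairs for one dose, ignoring strata. The plan gives no power, readmission rate or Day 30 in-hospital rate for the composite, so there is no stated figure to reproduce. The rates below are assumptions. The only guide is Phase 2a (Protocol 1.5.2), where the longest stay was 30.0 days among 7 control patients and 18.3 days among 14 Auxora patients. Reading the first as one patient still in hospital gives 1/7 = 14%. A true split of 55:45 (win ratio 0.55/0.45 = 1.22) is assumed as the starting point.

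**Net share of pairs reversed.**

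f = (placebo never discharged x Auxora readmitted) - (Auxora never discharged x placebo readmitted)

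Reported win ratio = (0.55 - f)/(0.45 + f)

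| Never discharged, placebo vs Auxora | Readmitted, each arm | f | Pairs of 2,916 | Win ratio |
|---|---|---|---|---|
| 5% vs 5% | 10% | 0.5% - 0.5% = 0 | 0 | 1.22 |
| 3% vs 0% | 5% | 0.15% | 4.4 | 0.5485/0.4515 = 1.21 |
| 7% vs 2% | 10% | 0.7% - 0.2% = 0.5% | 14.6 | 0.545/0.455 = 1.20 |
| 14% vs 0% | 15% | 2.1% | 61.2 | 0.529/0.471 = 1.12 |

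Each f is a ceiling for its row. It assumes that no affected pair is settled in tiers 1-3 and that every one would otherwise have gone the other way.

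**Cross-check by simulation** (4,000 per arm, tiers 1-3 all tied, median times to solid food of 72 and 144 h as in SAP 4, equal readmission hazard after discharge). The rule as written was compared with one that classes a stay to Day 30 with readmission.

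- 7% vs 2% never discharged, 10% readmission: 1.75 vs 1.79.
- 3% vs 0%, 5%: 1.88 vs 1.89.
- 5% vs 5%, 10%: 1.58 vs 1.58.
- 14% vs 0%, 20%: 1.81 vs 2.04.

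**Against sampling error.** Use the SAP 8.9 variance, unstratified and without tied pairs, with N = 108. The sum of squared scores is N(N² - 1)/3 = 419,868, so V = (54 x 54)/(108 x 107) x 419,868 = 105,948 and √V = 325.5. A 55:45 split gives T = 0.10 x 2,916 = 291.6 and Z = 0.90. The SAP formula then gives SE(log win ratio) = 0.2007/0.896 = 0.22 and a 95% CI of about 0.79 to 1.90. A net f of 0.5% lowers T by 2 x 0.005 x 2,916 = 29.2, or about 0.09 in Z. The 2.1% row lowers Z by 122.5/325.5 = 0.38.

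**The case against.** The strongest reply is that this is a narrow edge case. It needs one patient readmitted for AP, one never discharged, and ties on all three earlier tiers. Patients still in hospital at Day 30 may well be the ones who already lose on respiratory failure or necrosis. The same rule also works in Auxora's favour when the never-discharged patient is on Auxora. Prolonged stay is measured in SAP 8.7.3, and the primary analysis is the dose-response model for time to solid food in SAP 8.6. All of this stands, and it sets the severity.

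It could also be said that the SAP is merely silent on such patients. No sentence names them, but the binary wording still places them: they have no readmission, and their status is not unknown.

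A reader might infer three stronger things that the documents do not support.

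- That the composite penalises earlier discharge in general. It does not. A patient who goes home and stays home passes to tier 5 and can win there, and an arm leaving on Day 4 instead of Day 6 loses nothing by this route. Longer time at risk of readmission after an early discharge is a separate matter.
- That the win ratio would fall to 1.12. That row ignores offsetting pairs by setting Auxora's never-discharged share to zero, and it rests on one of seven Phase 2a controls. Phase 2a targeted patients with SIRS and hypoxemia. This trial does not require hypoxemia and excludes necrosis at screening, so 14% is probably too high.
- That the readmission proportion in SAP 8.7.4 is wrong because it keeps never-discharged patients in the denominator. A proportion over all MITT patients preserves the randomised comparison. Restricting it to patients discharged alive would condition on an outcome that treatment may affect.

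**Conclusion.** The point holds in a limited form. Applied as written, tier 4 and categories (g) and (h) place a patient still in the index stay at Day 30 above one readmitted for AP, without looking at time to solid food. The bias runs against a dose only when that dose leaves fewer patients in the index stay; with equal shares and equal readmission it vanishes. On the assumed middle rates the net effect is at most about 0.5% of pairs, 1.22 to about 1.20, well inside the sampling error for 54 per arm. The 1.12 figure is an outer bound, not an expectation. The rates are assumptions throughout, and nothing here shows that an earlier-discharging arm would lose overall. The reason to act is that the ranking is perverse and easily removed before unblinding. Low severity: a cheap improvement to a non-primary analysis.

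**What to change.** Redefine the tier-4 event in SAP 8.9 as "Rehospitalization for AP or pancreatic necrosis/necrotizing pancreatitis through the Day 30 Visit", or still in the index hospital stay at Day 30. Use the same definition in the pairwise scoring text and in categories (g) and (h), which currently name AP alone. Two patients who both have the event then tie and go to tier 5.

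This is better than calling tier 4 a tie whenever either patient was never discharged, because that rule creates cycles. Let A eat at 40 h and be readmitted, B eat at 100 h and go home without readmission, and C eat at 80 h and never leave. Under the tie rule B beats A on tier 4, A beats C on tier 5, and C beats B on tier 5. Under the combined event B beats both A and C on tier 4, and A beats C on tier 5, so the order is consistent.

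In SAP 8.7.4, keep the readmission proportion over all MITT patients and add the combined outcome as a supplementary summary. Do not add a rate restricted to patients discharged alive.

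The cost is about one sentence in 8.9, carried into the category wording, and one in 8.7.4. No new data are needed, since SAP 8.7.3 already identifies patients in hospital at Day 30. The one downside is that tier 4 no longer measures readmission alone, which the report should say.

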5. STUDY ENDPOINTS

5.1 Efficacy Endpoints:

- Primary endpoint
 - o Time to solid food tolerance
- Secondary endpoints:
 - Solid food tolerance at 48 hours, 72 hours, and 96 hours after the Start of First Infusion of Study Drug (SFISD) and at discharge
 - Time to medically indicated discharge
 - o Length of stay in the hospital
 - o Length of stay in the intensive care unit (ICU) for patients admitted to the ICU
 - o Re-hospitalization for acute pancreatitis (AP) by Day 30
 - o Change in severity of AP by CTSI score from screening to Day 30
 - o Development of pancreatic necrosis ≥30% and >50%
 - The persistence of SIRS ≥48 hours after the SFISD
 - o Incidence, severity, and duration of organ failure
 - o Mortality by Day 30
 - o Change in pain score and opioid use
- Exploratory endpoints:
 - o Development of infected pancreatic necrosis
 - Development of sepsis
 - o Hospital procedures for the management of pancreatic necrosis
 - Change in GCSI-DD score
 - o Change in albumin
 - o Change in absolute neutrophil count (ALC)/absolute lymphocyte count (ALC) ratio
 - o Change in IL-6 levels
 - o Change in urine neutrophil gelatinase-associated lipocalin (NGAL) levels

5.2 Safety Endpoints:

- The incidence of TEAEs and SAEs
- The intensity and relationship of TEAEs and SAEs
- Clinically significant changes in vital signs and safety laboratory results

5.3 Proof of Concept Composite Efficacy Endpoint:

The proof-of-concept efficacy analysis uses a hierarchical combination applying the method of Finkelstein-Schoenfeld (Finkelstein 1999) to:

- All-cause mortality at Day 30 Visit, and
- Persistent severe respiratory failure through Day 30 Visit, and
- Pancreatic necrosis ≥30% through Day 30 Visit, and
- Rehospitalization for AP through Day 30 Visit, and
- Time to solid food tolerance within 30 Days of the study

Protocol CM4620-203 CONFIDENTIAL Page 10 of 31

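### The proof-of-concept composite names its second tier in two ways (SAP 5.3, 8.9), and two pooled groupings may be changed after the primary analysis without a criterion or a fallback (SAP 8.9, 8.12)

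*SAP*

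**What the plan says.** **Tier 2.** SAP 5.3 lists "Persistent severe respiratory failure through Day 30 Visit, and". The numbered list that opens SAP 8.9 has instead "Severe respiratory failure through the Day 30 Visit, and". The FS scoring rule in 8.9 returns to the longer term: "The subject with persistent severe respiratory failure receives a -1 while the other without persistent severe respiratory failure receives +1". The FS comparison sequence, the missing-data rule and the pooling assumption also use the longer term.

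The win-ratio part of 8.9 mixes the two. Its lead-in reads "Categories (a), (c), (e), (g), and (i) represent Auxora wins based on all-cause mortality, persistent severe respiratory failure", but category (c) is "Severe respiratory failure on placebo but not on Auxora", category (d) is "Persistent severe respiratory failure on Auxora but not on placebo", and the next line begins "If a tie for severe respiratory failure".

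**Definitions.** SAP 8.7.8 defines severe respiratory failure as any invasive mechanical ventilation, or at least 48 hours of high-flow nasal cannula or non-invasive ventilation. Support during a procedure and non-invasive ventilation for sleep apnea do not count. *Persistent* means at least 48 hours in two places: Protocol 1.1, for organ failure in general, and the end of SAP 8.7.8, for new-onset failure on the modified Marshall score. Neither document defines *persistent severe*.

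**Pooling.** As a sensitivity analysis, SAP 8.9 pools the 1.25 and 0.625 mL/kg groups against 0.3125 mL/kg plus placebo. SAP 8.12 pools the same two upper groups against placebo for the subgroup analyses. Both assume that the two upper groups have similar effects. If that proves invalid after the primary analysis, 8.9 permits a change of grouping and 8.12 requires one. SAP 8.7.8 plans the 8.9 pooling for respiratory and multi-organ failure with no such clause.

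**The concern.** A programmer cannot tell from the SAP which event decides tier 2. The uncertainty reaches the FS test itself, because its component list and its scoring rules disagree. That test supplies the p-value for each dose against placebo, and its Z also gives the standard error of the log win ratio. If the win ratio were scored on one event and Z on the other, the confidence interval would combine two different analyses. Categories (c) and (d), if followed to the letter, would also count a broader event against placebo than against Auxora.

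The regrouping clauses raise a different matter. A default grouping is stated, but the conditions for leaving it and the grouping that replaces it are not. Both would be settled after unblinded results are known. Regrouping in 8.9 alone would also leave the parallel analysis in 8.7.8 on different groups.

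**Working it through.** The documents give no figure for this composite or for the pooled comparisons, so there is nothing to reproduce. All event rates below are assumptions.

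**1. Who changes class.** High-flow and non-invasive support already need 48 hours under 8.7.8. If *persistent* adds a 48-hour minimum, the two terms differ only for patients whose qualifying support was invasive ventilation lasting under 48 hours. If the terms are synonyms, nobody changes class.

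**2. One term used for both arms.** Either choice treats the arms alike, so the null win ratio is 1.00. What remains open is which test is run. I simulated 3,000 null trials per setting, with 54 per arm, four strata, a severe rate of 10% and the other rates of step 4, scoring FS once on each term. The two-sided 5% verdict differed in about 1 to 2% of trials when 10% of severe cases were ventilated for under 48 hours, and in about 3% when the share was 30%. Both versions kept an error rate near 5%, so this is disagreement between two valid tests and not inflated error.

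**3. Categories (c) and (d) taken literally, tier 2 only.** Let p be the severe rate, s the share of severe cases ventilated for under 48 hours, and q = p(1 − s). With identical arms, (c) has probability p(1 − p) and (d) has q(1 − q). At p = 0.10:
- s = 0: 0.0900/0.0900 = 1.00
- s = 0.10: 0.0900/(0.09 × 0.91) = 0.0900/0.0819 = 1.10
- s = 0.30: 0.0900/(0.07 × 0.93) = 0.0900/0.0651 = 1.38

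**4. Effect on the overall win ratio.** Assume independent components: mortality 3%, necrosis 10%, readmission 8%, and 5% never tolerating food.
- Deaths: 0.03 × 0.97 = 0.0291 for each side. Both alive: 0.97² = 0.9409.
- A pair that reaches tier 3 is won by a given side with probability 0.09 + 0.82 × [0.0736 + 0.8528 × 0.49875] = 0.4991.
- At s = 0.30, the share passing tier 2 is 1 − 0.0900 − 0.0651 = 0.8449, if uncategorised pairs are passed down.
- Wins: 0.0291 + 0.9409 × (0.0900 + 0.8449 × 0.4991) = 0.5106. Losses: 0.0291 + 0.9409 × (0.0651 + 0.8449 × 0.4991) = 0.4871. Ratio 1.048, or 1.049 if uncategorised pairs are dropped.
- The same steps give 1.02 at s = 0.10 and 1.03 at s = 0.20.

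**5. Effect on the interval.** SAP 8.9 sets SE = log(WR)/Z, so the 95% limits are exp[log(WR) × (1 ± 1.96/Z)]. A shifted win ratio moves the estimate and both limits. Whether the interval excludes 1 depends only on whether |Z| exceeds 1.96, so that conclusion does not change.

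**6. Regrouping.** I drew four equal arms 4,000,000 times under the null with z = 1.96, so the one-sided reference is 2.5% (half of the two-sided 5% in SAP 8.1.2). The fallbacks are my assumption.

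| Rule | 8.9 pooled comparison | 8.12 pooled comparison |
|---|---|---|
| Grouping kept | 2.5% | 2.5% |
| Switch only if the two upper doses differ at p < 0.05 on the same endpoint | 3.0–3.6% | 2.8–3.3% |
| Best of planned and fallback | 3.9–4.6% | 4.8% |

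The 8.9 fallbacks were 2.0 mg/kg against 0.5 mg/kg plus placebo, and 2.0 mg/kg against all others. The 8.12 fallbacks were one upper dose alone against placebo. If the 8.9 switch depended on the feeding contrast, the error would be 2.5 to 3.2% for a correlation of 0 to 0.8 with the composite. Choosing the best of three cut points along the dose order in 8.9 gives 6.2%, which shows how far the figure depends on the fallbacks assumed.

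**The case against.** The strongest reply is that nobody would program an asymmetric tier 2. SAP 8.9 describes the win ratio as moving down the hierarchy "until the first outcome is identified for which the outcomes differ between the patients", which means one outcome applied to both patients. The lead-in and the FS rules are symmetric too, and nearby wording is equally loose, such as necrosis above 30% against at least 30%. This stands: a reader might infer that the win ratio was built to favour Auxora, and the documents do not support that. It does not settle which of the two terms is meant.

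A reader might also infer that *persistent* has no meaning in this plan. It has one, in Protocol 1.1 and in SAP 8.7.8, and this lends some support to the 48-hour reading. Only the compound term lacks a definition.

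On regrouping, a reader might infer that 8.9 uses the feeding result to judge an assumption about respiratory failure. The sentence can equally be read as stating when the check happens; the analyses of respiratory failure in 8.7.8 could inform it. The feeding-trigger figures above apply only under the first reading.

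Finally, 8.12 is exploratory across eleven baseline variables with no stated multiplicity control, so locking the grouping would not fix its overall error rate. That is fair. For 8.12 the gain is transparency about which groups were planned.

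**Conclusion.** The point holds and is minor. The tier-2 event is not fixed by the SAP, and it feeds the per-dose FS p-values and win ratios. The effect is nil if the two terms are synonyms. If *persistent* adds 48 hours, it is confined to short invasive ventilation. The literal (c)/(d) reading would tilt the null win ratio to about 1.02 to 1.05 for short-ventilation shares of 10 to 30%, and would move its interval limits, but not whether the interval excludes 1. Those figures rest on a 10% severe rate and the other assumed rates; the documents give none of them.

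The regrouping clauses lack a criterion and a replacement. The illustrative one-sided error of about 3 to 5% depends on the fallback chosen. They touch a sensitivity comparison and exploratory subgroups only. It would be wrong to conclude that the gMCP-Mod primary test is affected, or that the per-dose comparisons are affected by regrouping.

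**What to change.** Amend the SAP before unblinding:
- Choose one respiratory-failure term, define it, and use it in 5.3 and everywhere in 8.9: list item 2, FS sequence and scoring rules, missing-data rule, win-ratio lead-in, categories (c) and (d), tie line and pooling assumption.
- State that the win ratio and the FS Z come from the same pair scores.
- Commit to reporting the pre-specified groupings in 8.7.8, 8.9 and 8.12 in all cases. Replace the adjustment sentences in 8.9 and 8.12 with a statement that any other grouping is post hoc and reported in addition.

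The cost is SAP wording only. The one small downside is that the pre-specified pooled result is still reported if the two upper doses prove dissimilar; the added post hoc grouping then sits beside it, labelled as such.
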